The Effects of Non –Surgical Periodontal Therapy on Glycemic Control and Periodontal Health in Diabetic Patients with Periodontitis (Randomized Controlled Clinical Trial)

NCT03783845

Document Date: December,11,2018

Research Protocol

Principal investigators' name (including position, affiliation, ID and contact details)	[name] Associated professor, Taibah University, KSA Assistant professor ,Tanta University, Egypt [contact] [contact] [name]
Co-investigators name(s) (including position, affiliation, ID and contact details)	None
Supervisor(s) name (if applicable) (including position, affiliation, ID and contact information)	None
Proposed School/ Discipline	Taibah University Tanta University

1. Project/ research title

The Effects of Non –Surgical Periodontal Therapy on Glycemic Control and Periodontal Health in Diabetic Patients with Periodontitis (Randomized Controlled Clinical Trial)

2. Project/ Research Summary

The aim of the present study is to monitor the clinical outcomes and the metabolic response of non-surgical periodontal therapy in patients with chronic periodontitis and uncontrolled type 2 diabetes.

Regarding clinical and metabolic parameters at baseline, no differences will be displayed between two groups. However, at 3-months follow-up period the patients within a test group will demonstrate better clinical outcomes than patients in a control group

3. Project/ Research details

3.1. Introductory background

The relationship between chronic periodontitis and diabetes has been the aim of the most intensive research [1]. Many studies suggested the concept of a two-way relationship between both diseases [2]. Type 2 diabetic(T2DM) patients show a higher extent, severity, and prevalence of chronic periodontitis than healthy subjects [3]. Accordingly, T2DM is considered a risk factor for chronic periodontitis [4]. Simpson et al .,(2010) observed that the deterioration of glycemic control attributed to chronic periodontitis over time[5]. Periodontal therapy can decrease local inflammation, the systemic entry of pro-inflammatory molecules and bacterial by-products such as lipopolysaccharides [2]. Simpson et al .,(2015) reported that many researches have studied the relationship between glycemic control and periodontal therapy (non-surgical modality) in the diabetic population and have demonstrated contradictory findings[6]. Several clinical trials recommended that more studies are necessary to clarify this link ([7]; [5]; [8]. Therefore, the aim of this clinical trial is to study the influence of non-surgical periodontal therapy on the glycemic level among T2DM patients with chronic periodontitis.

3.2. Research questions

Is the non-surgical periodontal therapy can improve glycemic control in type 2 diabetic patients with chronic periodontitis?

Null hypothesis is the non-surgical periodontal therapy doesn't improve glycemic control in type 2 diabetic patients with chronic periodontitis

3.3. Aims/Objectives of the project

The objective of the current clinical study is to evaluate the clinical and the metabolic effects of non-surgical periodontal therapy in patients with chronic periodontitis and uncontrolled type 2 diabetes.

3.4. Significant/Contribution to the discipline

In the present three- month controlled clinical study, an important aspect is a creation of an optimal non-surgical periodontal therapy (NSPT) (consist of OHI, SRP, combination of antibiotics, and antiseptics), versus no active therapy in control group, to enhance the probability of detection any impact of periodontal therapy on the HbA1C level. In the field, this maximization is unique because previous clinical trials either provided potentially effective periodontal therapy for control groups such as study of Engebretson et al., (2013) who stressed on oral hygiene instructions for control patients[9] or provided sub-optimal periodontal therapy such as study by Gay et al., (2014) who studied the impact of periodontal treatment composed of OHI and SRP alone[10].

In diabetic patients the data on the influence of periodontal treatment on metabolic control are contradictory. Some publications have reported that NSPT may improve

metabolic control [11], [5], [12], [13], [14]. However, in these patients, other studies cannot demonstrate significant improvement of glycemic control[7], [15], [16], [17], [6].

3.5. Theoretical framework and methods/approach

Methodology (The methodology, design, and materials, sample and sampling technique, description of study tools to be used).

A prospective, randomized controlled clinical trial will be conducted on two parallel groups with three months follow-up period. A convenient sample of 44 patients aged 40-70 will be recruited.

Test group (patients will give immediate periodontal therapy)

Control group (patients will give delayed periodontal therapy)

The subjects with uncontrolled type 2 diabetes (HbA1c from 7% to 9%) will be selected from attendants of Internal Medicine Outpatients Clinic, Tanta University Hospital and will be referred to Periodontology Department, Tanta University.

Closed envelopes technique will be used for random allocation of the study participants that identify to which group the subjects will be enrolled, using 1:1 allocation ratio. All patients will sign informed consent

Inclusion criteria

- Diagnosis of diabetes type 2 for more than five years
- Type 2 diabetes with HbA1c level from 7% to 9% at the last medical evaluation
- Age from 40 to 70 years
- No change of diabetes treatment over the previous three months
- Diagnosis with chronic periodontitis
- Minimum sixth permanent teeth excluding third molars
- Clinical attachment level (CAL) and pocket depth (PD) ≥ 4 mm in more than thirty percent of the sites

Exclusion criteria

- Pregnancy
- Alcoholism and smoking
- Presence of any systemic disorders other than hypertension and diabetes

- Diabetic major complications
- Antimicrobial therapies in the last 6 months
- Periodontal therapies in the last 6 months
- Allergy to metronidazole and amoxicillin

Intervention protocol

Periodontal therapy will include scaling and root planing (SRP), combination of systemic antibiotics[metronidazole 400 mg three times daily for two weeks and amoxicillin 500mg three times daily for two weeks] and oral hygiene instructions (OHI). Full-mouth SRP will be performed by the same specialist for all patients in a test group using ultrasonic apparatus and Gracey curettes in a single two-hour session. Local anesthesia will be applied when needed. SRP will be associated with subgingival irrigation by chlorhexidine 0.12% mouthwash. Immediately, after SRP, the administration of antibiotics combination will be started and patients will receive a free dental care products necessary for periodontal maintenance during a follow-up period (three months). For the patients within a control group delayed periodontal therapy will be performed using the same procedures that will be applied for the patients in a test group exactly after the end of follow up period (three months) because of ethical reasons. Therefore, within the control group, no periodontal therapies will be done during the follow-up.

Clinical and metabolic follow-up

A complete medical history, socio-demographic data, and information regarding daily dental care will be collected for all patients. Charting for the full-mouth periodontium using a periodontal probe will be performed by the same specialist. This includes PD, CAL, bleeding on probing and the visible dental plaque. The periodontal evaluation will be done at baseline and at three months. Blood will take from a peripheral vein to monitor HbA1c using high-performance liquid chromatography at baseline and at three months post-treatment.

Data analysis (The proposed method of data analysis)

Data will be coded, collected and analyzed using the SPSS software under Mac OS Majave Version 10.14. Descriptive statistics will be done using mean and standard deviations, followed by inferential statistics using the Fisher's exact test, Chi-Square test, student t- test and paired t-test. Significance was adopted at $p<0.05$ which will be used as a cutoff point to control for alpha error.

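### Does timing the HbA1c sample from treatment mean that controls are measured after their delayed therapy, or on a different clock from the test group?

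*Combined protocol and SAP*

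**What the plan says.** In section 3.5, under Clinical and metabolic follow-up, HbA1c is measured "using high-performance liquid chromatography at baseline and at three months post-treatment". The sentence makes no distinction between the groups. Shortly before it, the periodontal schedule is given without reference to treatment: "The periodontal evaluation will be done at baseline and at three months".

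The Intervention protocol in the same section sets the order of events. Control patients receive the test group's procedures "exactly after the end of follow up period (three months) because of ethical reasons", and the next sentence adds that "within the control group, no periodontal therapies will be done during the follow-up". Test patients are treated at once ("Test group (patients will give immediate periodontal therapy"). Scaling and root planing (SRP) is done "using ultrasonic apparatus and Gracey curettes in a single two-hour session". Then "Immediately, after SRP, the administration of antibiotics combination will be started", for a two-week course.

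Section 3.4 gives the intended contrast: periodontal therapy "versus no active therapy in control group, to enhance the probability of detection any impact of periodontal therapy on the HbA1C level". Sections 2, 3.5 and 3.7 all put the comparison or the follow-up at three months.

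**The concern.** Within follow-up, controls have no treatment from which three months could be counted, so the HbA1c sentence cannot be applied to them as it stands. There are two ways to fill the hole, and each looks damaging.

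- **Literal.** Count three months from the controls' delayed therapy. Their sample is then taken after the therapy under test. If therapy works equally in both groups and HbA1c does not drift over calendar time, the expected difference is zero and the chance of a significant result is the 5% alpha.
- **Milder.** Count from baseline in controls, and from SRP or the end of antibiotics in the test group. The test sample could then be drawn later after randomisation than the control sample.

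HbA1c answers the only research question (section 3.2) and is measured just twice, so the follow-up sample carries the whole comparison. The planned t-tests make no allowance for elapsed time.

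**Working it through.** The plan gives no figure of its own to reproduce here; the check is one of dates. I take three months as 13 weeks (91 days).

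**Step 1: the literal reading.**

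- Control therapy comes no earlier than week 13 (section 3.5, Intervention protocol).
- Three months after SRP: 13 + 13 = week 26.
- Three months after the end of the two-week antibiotic course: 13 + 2 + 13 = week 28.

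Both dates lie outside the study, since section 3.7 sets follow-up at three months and section 3.5 describes two parallel groups followed for three months. Both also contradict the untreated comparator of section 3.4. The sentence on control therapy in section 3.5 says outright that none is given during follow-up. The summary in section 2 compares the groups at the three-month visit. Against all of these, the literal reading has one phrase in its favour. The 5% power figure belongs to that reading and falls with it.

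**Step 2: the milder reading.** Let g be the weeks from baseline to SRP. Let a be 0 if time runs from SRP and 2 if it runs from the end of antibiotics. The test sample falls at week g + a + 13 and the control sample at week 13, so the difference is g + a.

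| Assumed g (weeks) | Difference, counted from SRP | Difference, counted from end of antibiotics |
|---|---|---|
| 0 | 0 | 2 |
| 1 | 1 | 3 |
| 2 | 2 | 4 |
| 4 | 4 | 6 |

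The document does not state g; the values above are assumptions. With g = 0 and a = 2 the difference is 14/91 = 15% of follow-up.

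**Step 3: which cell does the text support?** Test therapy is described as immediate, which points to g at or near 0. SRP is completed in one session, so it has a single date. Right after that session patients are given care products for the three months of follow-up, which ties the start of follow-up to SRP and so points to a = 0. Nothing in the text starts the clock at the end of the antibiotics. The best-supported cell is a difference of 0 weeks.

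**Step 4: what would a difference cost?** The 15% is a share of calendar time. Turning it into bias in HbA1c would need a rate of change of HbA1c around month 3, and the document gives none. No loss of power or shift in the estimate can be derived from it.

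**The case for a change.** The strongest case for a change is that the reader has to override the sentence governing the key outcome in order to reach the sensible plan, for half of the 44 patients (22 per group at 1:1). Immediate therapy is not tied to the date of the baseline sample. Patients are referred from the internal medicine clinic to another department, so a wait is conceivable. Therapy is defined to include the antibiotics, so the end of treatment has two possible dates. No visit window is given. With only two HbA1c samples, unequal timing could not be corrected afterwards, and tidying the wording would cost a sentence.

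Part of this stands. The phrase has no meaning for controls during follow-up, it does not match the periodontal schedule beside it, and the interval from baseline to SRP and the visit window are unwritten.

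It does not show that the trial would be run wrongly. The order of events for controls is stated outright in the same section, and a single month-3 visit for blood and probing in both groups is the natural way to carry out the plan. A harmful gap between the groups needs a delay or a starting point that the text does not contain, and its effect on HbA1c has not been shown.

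**Conclusion.** The concern does not call for a change. The inconsistency is real but clerical: the HbA1c sentence was written with the test group in mind. Taken as a whole, the plan compares treated patients with still-untreated controls at about month 3, which is a sound contrast.

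The timing difference between groups is 0 weeks on the best-supported reading and 2 weeks if time were counted from the end of antibiotics. It reaches 1 to 6 weeks only under assumed waits of 1 to 4 weeks before SRP. The sample at month 6 and the 5% power figure are excluded by the document's own statements.

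This rests on two assumptions: that immediate therapy means SRP at or near baseline, and that the month-3 assessments in controls precede the delayed therapy, as the order set out in section 3.5 implies. A common anchor and window would record what the investigator would do anyway, with no demonstrated effect on the estimate, the error rate or the power.

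### The between-arm test for HbA1c, PD and CAL is left open (3-month value or change) and ignores baseline; ANCOVA on the same data would usually be more precise

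*Combined protocol and SAP*

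**What the plan says.** The whole inferential plan is one sentence under Data analysis in section 3.5, which lists Fisher's exact test and then "Chi-Square test, student t- test and paired t-test", with a 0.05 cutoff. No test is assigned to an outcome, a time point or a comparison.

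The same section, under Clinical and metabolic follow-up, collects both measurements that a baseline-adjusted analysis needs. For PD and CAL, "The periodontal evaluation will be done at baseline and at three months". For HbA1c, blood is drawn "to monitor HbA1c using high-performance liquid chromatography at baseline and at three months".

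The closest text to a between-arm comparison is an expectation in section 2: "at 3-months follow-up period the patients within a test group will demonstrate better clinical outcomes than patients in a control group". Section 3.2 asks whether therapy improves glycaemic control, but names no analysis. ANCOVA, regression or any other baseline adjustment appears nowhere in the document.

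**The concern.** The trial's conclusion rests on the difference between arms at three months. The paired t-test uses baseline, but only within one arm, so it does not estimate the treatment effect. That leaves the Student t-test, which could be run on the 3-month value or on the change.

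Two things follow.

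- **Precision.** Neither t-test makes the best use of baseline. The 3-month-value test discards it, and the change score subtracts it in full whether or not it predicts follow-up. With 44 patients and no sample-size calculation, the interval for the treatment effect is usually wider than the collected data allow.
- **An open choice.** Which t-test has more power depends on a correlation that will be visible only in the data. Choosing the scale afterwards also inflates the false-positive rate.

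This is not a claim of bias. Under randomisation either t-test is unbiased, and chance baseline imbalance is already reflected in its standard error.

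**Working it through.** **Inputs from the protocol (section 3.5).** "A convenient sample of 44 patients aged 40-70 will be recruited"; with 1:1 allocation this gives n = 22 per arm. The significance level is 0.05; sidedness is not stated and is taken as two-sided.

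**Assumptions, because the documents give no figures.** Complete data; the same baseline slope in both arms; follow-up SD = 1; baseline SD = k; baseline-to-3-month correlation r. The sample size of 44 cannot be reproduced, since no effect size, SD or power is stated.

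**Variance of the arm difference, relative to a t-test on the 3-month value**

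- 3-month value: 1
- Change: 1 + k² − 2rk = (1 − r²) + (k − r)²
- ANCOVA: (1 − r²) × (1 + 1/(2n − 4)) = (1 − r²) × (1 + 1/40) = 1.025(1 − r²)

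Example at r = 0.5, k = 1: change = 1 + 1 − 1 = 1; ANCOVA = 1.025 × 0.75 = 0.77.

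| r | ANCOVA / 3-month value | ANCOVA / change, k = 1 | ANCOVA / change, k = 0.7 |
|---|---|---|---|
| 0.2 | 0.98 | 0.62 | 0.81 |
| 0.3 | 0.93 | 0.67 | 0.87 |
| 0.5 | 0.77 | 0.77 | 0.97 |
| 0.7 | 0.52 | 0.87 | 1.025 |
| 0.8 | 0.37 | 0.92 | 1.00 |

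**Worst case.** The change factor is never below 1 − r², so ANCOVA/change is at most 1.025, reached when k = r. ANCOVA/3-month value is at most 1.025, reached at r = 0. ANCOVA overtakes the 3-month-value test at r = √(1 − 1/1.025) = 0.16. The widest possible relative interval is √1.025 × t(0.975, 41)/t(0.975, 42) = 1.013, that is, 1.3% wider.

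**Power for an assumed effect of 0.6 SD** (k = 1; noncentral t with 42 df, or 41 for ANCOVA)

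| r | 3-month value | Change | ANCOVA |
|---|---|---|---|
| 0.2 | 49% | 34% | 50% |
| 0.3 | 49% | 38% | 52% |
| 0.5 | 49% | 49% | 60% |
| 0.7 | 49% | 71% | 77% |
| 0.8 | 49% | 87% | 89% |

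Simulation (40,000 trials per setting) matched the variance ratios to within 0.01. Each of the three tests, used alone, held its type I error at 4.8% to 5.3%.

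**Where the lost precision comes from.** The chance baseline difference has standard error √(2/22) = 0.30 SD and exceeds 0.3 SD in 32% of trials.

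**Cost of the open choice.** In simulated null trials, significance on either the 3-month value or the change occurred in about 9% to 10% of trials with equal SDs, and about 8% with k = 0.7, for a single outcome. If within-arm paired tests were read as the comparison, a significant test arm beside a non-significant control arm occurred in about 15% to 25% of null trials in which both arms shifted by 0.3 to 0.5 SD.

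**The case against.** The strongest reply is that only the open contrast is a defect. A Student t-test on either scale is valid, so pre-specifying one would close that gap, and preferring ANCOVA is a choice between sound methods. This is right about validity. A single pre-specified t-test would remove the selection problem, but it would still leave precision unused in a small trial.

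A second point is that the gain is unknown and may be slight. Against the 3-month-value test the interval is only 0.7% narrower at r = 0.2 and 3.4% narrower at r = 0.3, against 12% at r = 0.5. This stands. HbA1c may be the weaker case, because entry requires "Type 2 diabetes with HbA1c level from 7% to 9% at the last medical evaluation", which could lower both the baseline SD and r. That range applies to an earlier assay, not the trial's own baseline, so how far it restricts the baseline spread is uncertain. The k = 0.7 column is a sensitivity case, not an estimate. Its cells at r = 0.7 and 0.8 imply slopes of 0.7/0.7 = 1.0 and 0.8/0.7 = 1.14, so the cells where the gain vanishes are demanding ones.

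Third, equal slopes may fail for PD and CAL, since one arm is treated and the other is not during follow-up. A simulation with slopes of 0.2 and 0.8 kept the ANCOVA type I error at 5.1% and the variance ratio near 0.76, so this does not undo the case.

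Finally, section 2 leans towards a 3-month comparison. It is a prediction of clinical outcomes, however, and does not define an analysis for HbA1c or for the periodontal measures.

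**Conclusion.** The concern holds. The protocol leaves the between-arm contrast undefined and plans no use of baseline in it, although baseline will be available for all three outcomes. A pre-specified Student t-test would be valid, so this is a matter of efficiency and of closing an analysis choice, not of bias. It is something the sponsor should change; it is not fatal.

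The size of the gain depends on r and the SD ratio, which the documents do not give. Over r = 0.2 to 0.8, the variance ratio runs from 0.98 down to 0.37 against the 3-month value, and from 0.62 to 0.92 against change with equal SDs. The possible loss is bounded at 2.5% of variance whatever r and the SD ratio are, given complete data and a common slope. Confidence in the size of the gain is moderate; confidence that the contrast is unspecified is high.

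**What to change.** In section 3.5, Data analysis:

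- Replace the between-arm Student t-test for HbA1c, PD and CAL with ANCOVA: 3-month value as outcome, arm as factor, and the baseline of the same variable as covariate.
- Report the adjusted difference between arms with its 95% confidence interval.
- State that paired t-tests describe change within each arm and are not used to compare arms.
- Apply the same model to bleeding on probing and visible plaque only if they are summarised as continuous per-patient measures; the section gives no scale for them.

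This takes a few sentences and no new data or visits. It uses one residual degree of freedom (42 to 41) and, if baseline carries no information, 2.5% of variance. It should be written in before any between-arm results are seen.

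### The claimed alpha control has no single test to attach to: no primary outcome is named, and neither t-test is assigned to the glycaemic null hypothesis

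*Combined protocol and SAP*

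**What the plan says.** The glycaemic question leads in three places of the combined protocol and SAP. Section 3.1 gives the aim as "to study the influence of non-surgical periodontal therapy on the glycemic level among T2DM patients with chronic periodontitis". Section 3.2 states the only null hypothesis: "Null hypothesis is the non-surgical periodontal therapy doesn't improve glycemic control in type 2 diabetic patients with chronic periodontitis". Section 3.4 explains that the contrast with an untreated control group was chosen "to enhance the probability of detection any impact of periodontal therapy on the HbA1C level".

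Other places are broader. Section 2 sets out "to monitor the clinical outcomes and the metabolic response of non-surgical periodontal therapy", and its prediction for three months concerns clinical outcomes only. Section 3.3 names clinical and metabolic effects together and ranks neither. No section labels any outcome primary or secondary.

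Under Clinical and metabolic follow-up, section 3.5 provides for blood sampling "to monitor HbA1c using high-performance liquid chromatography at baseline and at three months post-treatment". It describes the periodontal charting as follows: "This includes PD, CAL, bleeding on probing and the visible dental plaque".

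Under Data analysis, the same section lists Fisher's exact and chi-square tests and the "student t- test and paired t-test" as inferential methods. It assigns none of them to an outcome, contrast or time point. It then gives p<0.05, "which will be used as a cutoff point to control for alpha error".

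**The concern.** A per-test cutoff of 0.05 limits the error rate of a hypothesis only if one test decides that hypothesis. HbA1c can reasonably be inferred as the lead outcome, but that inference does not settle the test. HbA1c is measured twice, so a Student t-test could compare the arms on the 3-month value or on the change from baseline. A paired t-test could also be run within the test arm.

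The null in section 3.2 names no contrast, time point or control group. A significant fall within the treated arm could therefore be reported as rejecting it, although such a fall compares nothing with the control arm. That would discard the untreated comparison that section 3.4 presents as the design's strength. If the deciding test can be chosen after the data are seen, the stated alpha control does not hold.

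**Working it through.** **Inputs from the documents.** Section 3.5 gives 44 patients at 1:1, so 44 / 2 = 22 per arm; HbA1c at baseline and three months; and a cutoff of 0.05. The plan does not say whether tests are one- or two-sided. There is no error-rate calculation in the plan to reproduce beyond the cutoff itself.

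**Assumptions (the documents give no values).** Normal data with equal SDs; no treatment effect; baseline to 3-month correlation r of 0.3, 0.5 and 0.7; two-sided 0.05 tests. A change common to both arms is set at 0, then at a fall of 0.2 SD or 0.5 SD.

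**What is counted.** The null in section 3.2 is directional, so only significant results in favour of therapy count as false rejections. One fixed two-sided test then has a rate of 0.05 / 2 = 2.5%. Where several tests may decide, the rate is the chance that at least one is significant in the favourable direction. It was simulated with at least 100,000 trials per setting (42 df for the two-sample tests, 21 df for the paired test).

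| Which test may reject the null | No common change | Both arms fall 0.2 SD | Both arms fall 0.5 SD |
|---|---|---|---|
| One fixed between-group test | 2.5% | 2.5% | 2.5% |
| 3-month value or change, between groups | about 4.4–4.7% | unaffected | unaffected |
| Value, change, or test-arm paired test | about 6.0–6.3% | about 14–23% | about 48–83% |

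Ranges run from r = 0.3 to r = 0.7.

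**Why only the last row moves.** A change common to both arms cancels in any between-group difference. In the paired test it does not. With the SD of HbA1c set to 1, the SD of the change is √(2(1 − r)), so the expected paired t is about drift × √22 / √(2(1 − r)), with √22 = 4.69:

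- Drift 0.2: 0.94 / 1.18 = 0.79 at r = 0.3; 0.94 / 1.00 = 0.94 at r = 0.5; 0.94 / 0.775 = 1.21 at r = 0.7.
- Drift 0.5: 2.35 / 1.18 = 1.98 at r = 0.3; 2.35 / 1.00 = 2.35 at r = 0.5; 2.35 / 0.775 = 3.03 at r = 0.7.

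The two-sided 5% critical value on 21 df is about 2.08. A modest common fall therefore brings the within-arm test close to significance or past it, with no effect of therapy.

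**Choice among the valid between-group tests.** Each of the three holds its nominal level when fixed in advance. They differ in precision. Relative to the unadjusted 3-month comparison (variance 1):

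- Baseline-adjusted (ANCOVA): 1 − r² = 0.91, 0.75 and 0.51 at r = 0.3, 0.5 and 0.7.
- Change score: 2(1 − r) = 1.40, 1.00 and 0.60.

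ANCOVA has the smallest variance at every assumed correlation, apart from the loss of one degree of freedom.

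**The case against.** The strongest reply is that the plan is less open than it looks. In a two-arm parallel trial the Student t-test is naturally the between-group test, and the paired t-test can only be the comparison of baseline with three months within an arm. Section 3.4 frames the HbA1c question against an untreated control, and section 2 compares the two groups at baseline and at three months. No section proposes to decide the null on a within-arm result. This largely stands: a between-group HbA1c test is the best reading. It still leaves value or change undecided, and the paired test remains listed as inferential with nothing to keep it from deciding the hypothesis.

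A second reply is that 4.4–4.7% is still below 5%. That holds only if two-sided tests at 0.05 are judged against a one-sided allowance of 5%. On a one-sided reading each single test already uses 5%, and allowing either of two different tests must exceed it.

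A third reply is that the large figures come from assumed drift. That is right. The documents give neither its size nor its direction, and a common rise would make a false improvement within the test arm less likely, not more.

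A reader might also infer stronger points that the documents do not support:

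- *Error inflation across all five measured outcomes.* The only stated null is glycaemic, no section says that success on any one outcome would suffice, and true nulls are unlikely for the periodontal measures.
- *Error rates that include worsening, or a significant change in the control arm alone.* Neither could reject a null that therapy brings no improvement.
- *A contradiction between the joint objective and the glycaemic null.* Sections 2 and 3.3 are compatible with a single primary test.

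**Conclusion.** The omission is certain from the text: there is no named primary outcome and no named deciding test, yet alpha control is claimed. The claim holds for one prespecified between-group HbA1c test and not otherwise.

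The size is modest if only the form of the between-group test is open: 2.5% becomes about 4.4–4.7% for false results favouring therapy. It is about 6% if the test-arm paired test may also decide and HbA1c is otherwise stable. It becomes serious only if both arms fall for reasons unrelated to therapy: about 14–23% at 0.2 SD and 48–83% at 0.5 SD. All these figures rest on assumed correlations, assumed drift and the assumption that any favourable test would be accepted. They show what the wording permits, not what the sponsor intends. The point should be fixed, and confidence is higher in the omission than in its size.

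**What to change.** In section 3.5, Data analysis:

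- Name the between-group comparison of 3-month HbA1c, adjusted for baseline HbA1c by ANCOVA, as the single primary test at two-sided 0.05.
- State that the null in section 3.2 is decided by that test alone.
- Make pocket depth, attachment level, bleeding and plaque secondary outcomes, and within-arm paired t-tests descriptive only.
- Limit the sentence on alpha control to the primary test.

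If the sponsor prefers a test already listed, a Student t-test on change also holds 5% when fixed in advance, with less precision as shown above. Sections 2 and 3.3 need not be rewritten.

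The cost is protocol wording. Both HbA1c values are already collected, so visits, measurements and sample do not change. The downside is that periodontal and within-arm results can no longer stand as confirmatory evidence.
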